6.2 Covariate and Subgroups

Safety

Age (under 65, over 65) is used as subgroup for the analysis of treatment emergent adverse event.

Efficacy

The methodology described in the protocol for the efficacy analyses is a mixed model with repeated measures (MMRM). In light of the fact that the efficacy measurements were recorded at visit 2 and visit 6 only, there are no repeated measures. Therefore, the MMRM model described in the protocol cannot be applied to these analyses. The efficacy analyses will be conducted as an analysis of covariance (ANCOVA).

The model will include Baseline values as a covariate and dose and site as factor variables.

Baseline is defined as end of Screening Placebo Run-in for all efficacy analyses (Visit 2).

Exploratory efficacy analysis will be performed based on the baseline severity of incontinence episodes, as defined in section 5.4.2. Patients will be divided in 2 groups according to the median number of incontinence episodes.

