4.1 Inclusion Criteria

Subjects aged 18 to 70 will be **eligible for inclusion** in this study if all the following criteria apply:

1. Willing to provide written informed consent
2. Have symptoms of urinary incontinence for at least 3 consecutive months
3. For male subjects: If subject has undergone any prostate procedure, this must have occurred at least 6 months prior to screening
4. Have at least 7 incontinence episodes per week in the diary entries for the Screening Placebo Run-In Period
5. Subject is ambulatory and able to use the toilet independently
6. If subjects use pelvic floor exercises, subjects must have been on a stable exercise and activity regime for at least 3 months prior to screening and that regime must remain stable during the treatment period
7. Subject has a body mass index (BMI) $\geq 19 \text{ kg/m}^2$ but $\leq 35 \text{ kg/m}^2$ (BMI=weight [kg] / height [m^2])
8. Subjects must have a pre-dose mean systolic/diastolic blood pressure of $\leq 140/90 \text{ mmHg}$ before randomization can occur
9. For female subjects: Must not be pregnant, lactating, or actively trying to become pregnant. Subjects who are premenopausal and of childbearing potential must have a negative pregnancy test at Screening (serum) and at Day 0 (urine) and must use a medically acceptable and effective method of birth control for the duration of the study, which can include:
 - a. Having a male partner who is sterile prior to the female subject's entry into the study and is the sole sexual partner for that female subject
 - b. Use of double-barrier methods of contraception; condoms with the use of caps (with spermicide) and intra-uterine devices are acceptable
 - c. Use of hormonal contraceptives (oral, depots, patches, etc.) with double-barrier methods of contraception as outlined above

- d. True abstinence: When this is in line with the preferred and usual lifestyle of the subject (period abstinence [eg, calendar, ovulation, symptothermal, post-ovulation methods] and withdrawal are not acceptable methods of contraception)
- 10. Subjects taking oral contraceptives or hormone replacement therapy (women) or hormone adjuvant therapy (men) must have a stable dose and regimen for ≥ 3 months prior to entry into the study

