5.4 Efficacy Variables

Bladder Diary Questions

The bladder diary will be completed daily for the 7 days prior to visit 2 and visit 6, to record the number of incontinence episodes and whether these were nocturia events. If a subject has multiple events in 1 day, each event will preferably be entered separately. The number of incontinence pads used will also be recorded in the diary.

Percentage change in number of incontinence episodes in a week

The number of incontinence episodes entered into the eCRF is the total number of events a subject recorded during the 7day period prior to visit 2 and visit 6. This number will be directly used in the calculation of % change in number of incontinence episodes in a week

Number of Incontinence Episodes/24 hours (daily average)

The number of incontinence episodes entered in the eCRF will be divided by 7 to compute the number of episodes/24 hours (daily average). This consideration follows the assumption that the bladder diary will be filled by the subject for the 7 days prior to Visit 2 and Visit 6 and that the patient entered all episodes occurred in this period. Therefore, the following formula will be used:

$$\text{Number of Incontinence episodes / 24 hours} = \frac{\text{Number of incontinence episodes recorded}}{7}$$

Number of Nocturia Episodes in a week

The number of nocturia episodes entered in the eCRF is the total number of nocturia episodes a subject recorded during the 7day period prior to Visit 2 and Visit 6. The value entered in the eCRF will be used in the efficacy analysis of nocturia episodes without any adjustment.

Number of Incontinence Pads per week

The number of incontinence pads entered in the diary represents the number of pads used in a week, therefore the value entered in the eCRF will be used in the analysis without any adjustment.

This consideration follows the assumption that the bladder diary is completed by the subject for the 7 days prior to Visit 2 and Visit 6 and that the patient entered all pads used in this period.

Proportion of subjects who become continent

A subject is defined as continent if he/she has no incontinence episodes.

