6.3 General Methodology

Safety

Safety data will be presented and analysed using the Safety Population.

The primary safety analyses include all treatment emergent adverse events defined as any AE started after Visit 2. The analysis will be carried out with point estimates and Clopper Pearson 95% confidence intervals.

Descriptive statistics will be provided for all variables in the summary tables by treatment group according to the type of variable summarised.

Quantitative variables will be summarised by using n (number of subjects per group), arithmetic mean, standard deviation (SD), median and range (minimum and maximum).

Categorical variables will be summarised by using frequency distributions and percentages.

The number of Adverse Events and the number and the percentage of patients experiencing those events, will be summarised by treatment group. Differences between groups will be evaluated using Chi-square test or Fisher's exact test. Subgroup analysis of differences between groups of AEs will be performed separately for patients who had an adverse event while on the 10mg dose (AE started from Visit 2 and Visit 3), 20 mg dose (AE started from Visit 3 and Visit 4) and 30 mg dose (AE started from Visit 4 and Visit 6). Subjects with adverse events who deviated from the protocol dosage will be highlighted in the footnotes.

Shift tables will be used to describe the evaluation of clinical significance for laboratory values, 12-Lead ECG and physical examination.

For all analyses, hypothesis testing will be carried out at the alpha = 0.05 level (two-sided) when comparing treatments. P-values will be rounded to three decimal places. Statistical significance will be declared if the rounded p-value will be less than or equal to 0.05.

Efficacy

For the PP efficacy analysis of incontinence episodes, only valid efficacy endpoints at Visit 6 will be used. For the ITT efficacy analysis of incontinence episodes, valid and imputed endpoints at Visit 6 will be used. The imputation method is described in section 6.1. No LOCF from baseline will be used for any efficacy analysis.

Descriptive statistics will be provided for all variables in the summary tables by treatment group according to the type of variable summarised.

Quantitative variables will be summarised by using n (number of subjects per group), arithmetic mean, standard deviation (SD), median and range (minimum and maximum).

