6.9 Efficacy Analyses

Efficacy will be assessed by the number of urinary incontinence episodes. There is only one hypothesis so there will be no adjustment for multiplicity.

The efficacy analysis will be performed on the ITT and PP populations.

There will not be an adjustment for multiple comparisons for these efficacy analyses.

Baseline for all efficacy endpoints will be defined as the last week of the Screening Placebo Run-In Period (Visit 2). The final measurement (endpoint) will be defined as Week 8 (Visit 6).

1. Percentage change from end of the Screening Placebo Run-In Period to Week 8 in the number of incontinence episodes in a week

The efficacy analysis planned is an analysis of covariance model (ANCOVA). Percentage change in the number incontinence episodes/week is the response variable. The factor variables will be dose and centre. If the center effect is significant, summary statistics will be presented to describe the effect. The covariate will be end of the Screening Placebo Run-In Period episodes of incontinence.

The percentage change, $\%UIE_i$, for subjects in each arm, is expressed as the ratio of the total number of urinary incontinence episodes in a week between final measurement ($UIE_{i,end}$) and baseline ($UIE_{i,base}$)

$$\%UIE_i = \frac{UIE_{i,end}}{UIE_{i,base}}$$

Since percentage change from baseline does not have the properties of additivity and symmetry, it will be log-transformed, and the response variable will be the natural logarithm of the ratio of Week 8 (Visit 6) to Baseline, as shown below:

$$\log(\%UIE_i) = \log\left(\frac{UIE_{i,end}}{UIE_{i,base}}\right)$$

The hypothesis test being conducted is as follows:

$$\begin{aligned} H_0: \log(\%UIE_{\text{Litoxetine}}) - \log(\%UIE_{\text{Placebo}}) &= 0 \\ H_1: \log(\%UIE_{\text{Litoxetine}}) - \log(\%UIE_{\text{Placebo}}) &\neq 0, \end{aligned}$$

This is equivalent to testing the hypothesis:

$$H_0: \log\left(\frac{\%UIE_{Litoxetine}}{\%UIE_{Placebo}}\right) = 0$$

The result of the ANCOVA model will be expressed as log % and then back transformed to percentage change. Therefore, H_0 can be interpreted as:

$$H_0: \frac{\%UIE_{Litoxetine}}{\%UIE_{Placebo}} = 1$$

This makes the actual statistics:

$$\delta = \log(\%UIE_{Litoxetine}) - \log(\%UIE_{Placebo}) = \log\left(\frac{\%UIE_{Litoxetine}}{\%UIE_{Placebo}}\right)$$

When back-transformed, this is expressed as follows:

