$$\Delta = \exp\left(\log\left(\frac{\%UIE_{Litoxetine}}{\%UIE_{Placebo}}\right)\right) = \frac{\%UIE_{Litoxetine}}{\%UIE_{Placebo}}$$

$\%UIE_i$ is the ratio of the total number of urinary incontinence episodes in a week at endpoint (Visit 6) ($UIE_{i,end}$) to the total number of urinary incontinence episodes in a week at baseline ($UIE_{i,base}$) for arm i , with i equal to Litoxetine or Placebo.

An ANCOVA will be performed to compare δ to 0; the test will provide an appropriate p-value with a significance level alpha equal to 0.05. This p-value will be computing the probability of observing a difference among arms.

Numbers of incontinence episodes equal to 0 (not missing) will be imputed as 0.4 to allow for the log transformation.

2. Absolute change from end of the Screening Placebo Run-In Period to Week 8 in the number of incontinence episodes/24 hours (daily average)

The analysis planned is an analysis of covariance model (ANCOVA). Absolute change in the total number of incontinence episodes/24 hours is the response variable. The factor variables will be dose and centre. The covariate will be end of the Screening Placebo Run-In Period episodes of incontinence.

Number of incontinence episodes/24 hours will be computed as Total Number of incontinence episodes recorded during the 7-day period and entered in the eCRF divided by 7, as defined in Section 5.4.

The hypothesis test being conducted is as follows:

$$H_0: \Delta UIE_{Litoxetine} - \Delta UIE_{Placebo} = 0$$
$$H_1: \Delta UIE_{Litoxetine} - \Delta UIE_{Placebo} \neq 0$$

Where ΔUIE_i is the absolute change, for subjects in arm i , in the number of incontinence episodes/24 hours as defined above from baseline ($UIE_{i,base}$) to the final measurement ($UIE_{i,end}$):

$$\Delta UIE_i = UIE_{i,end} - UIE_{i,base}.$$

Where i goes from 1 to 2 and it represents the 2 arms: Litoxetine and Placebo.

3. Proportion of subjects who become continent at Week 8

A subject is defined as continent if s/he has no incontinence episodes at Visit 6 (Week 8). Frequencies will be used to describe the proportion of subjects who are continent at Week 8. The proportion will be computed on the total number of subjects for each arm at baseline. The category Missing will be included in the analysis, to consider subjects who do not attend the visit or who have missing values for that visit.

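### The log-ratio efficacy ANCOVA appears to adjust for the untransformed baseline count; stating log baseline instead is a free but modest efficiency gain

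*SAP*

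**What the plan says.** SAP 6.9 point 1 moves the first efficacy endpoint to the log scale and gives its reason: "Since percentage change from baseline does not have the properties of additivity and symmetry, it will be log-transformed". It then states that "the response variable will be the natural logarithm of the ratio of Week 8 (Visit 6) to Baseline". The model has dose and centre as factors, and "The covariate will be end of the Screening Placebo Run-In Period episodes of incontinence".

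SAP 6.2 gives the general rule for the efficacy ANCOVAs: "The model will include Baseline values as a covariate and dose and site as factor variables". Neither section says whether the baseline covariate is logged or raw. SAP 5.4 says of the weekly total in the eCRF that "This number will be directly used in the calculation of % change in number of incontinence episodes in a week", and no section defines a logged baseline.

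Two other provisions matter. Entry requires subjects to "Have at least 7 incontinence episodes per week in the diary entries for the Screening Placebo Run-In Period" (Protocol 4.1), and no upper limit is set. For zeros, "Numbers of incontinence episodes equal to 0 (not missing) will be imputed as 0.4 to allow for the log transformation" (SAP 6.9 point 1).

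The same model is reused by reference in SAP 6.9.1 points 1, 3 and 5, in 6.9.2 point 1, and for nocturia in 6.9 point 5. The nocturia item also names the incontinence baseline, not the nocturia baseline, as its covariate.

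**The concern.** The response is log(end) − log(base). If Week 8 counts regress toward the mean on the log scale, the response is linear in log(base). A straight line in the raw count then leaves part of the baseline effect in the residual. Counts with a floor of 7 and no ceiling are likely to be right-skewed. On the raw scale a few high counts would then carry much of the information on the baseline slope.

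Baseline is the only prognostic covariate besides site, and about 60 evaluable subjects are expected at 2:1. What is at stake is the width of the interval for the litoxetine/placebo ratio and how fully a chance baseline imbalance is corrected. The validity of the comparison is not at stake. The plan's own reason for taking logs of the response is also not carried through to the covariate.

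**Working it through.** **Inputs from the documents.** Response, covariate and zero rule: SAP 6.9 point 1. Baseline minimum of 7 per week: Protocol 4.1. Evaluable subjects: 60 at 2:1 (SAP 3.1 and 3.2), so 40 and 20. Tests are two-sided at 0.05 (SAP 6.3). The documents give no baseline distribution, residual SD, baseline-to-endpoint slope or efficacy power. The only design figure, ±14%, concerns safety event rates, so there is no efficacy figure to reproduce.

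**Step 1: an algebraic check that needs no assumptions.** Let y = log(end) − log(base). With log(base) as covariate, subtracting log(base) from the response changes only the baseline coefficient, by −1. The treatment coefficient is identical to that from an ANCOVA of log(end). With raw base as covariate, log(base) is not in the model space, so the two treatment estimates differ. In simulated data (40 vs 20) they agreed to 1e-14 with log baseline. With raw baseline they differed on average by 0.03 to 0.08 on the log scale, for an assumed log-SD of baseline of 0.5 to 1.0.

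**Step 2: approximate size by formula.** Assume log(end) = a + b·log(base) + treatment + error with SD σ. With raw baseline, the part of log(base) not linear in base joins the residual:

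variance ratio (raw/log) ≈ 1 + (1 − b)²·V·(1 − r²)/σ²

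Here V is the variance of log baseline and r is its correlation with the raw count. Assume a log-normal baseline with median 14 and log-SD s, truncated at 7. With α = ln(7/14)/s and λ = φ(α)/(1 − Φ(α)), V = s²(1 + αλ − λ²). This gives V = 0.185, 0.307 and 0.540 for s = 0.5, 0.7 and 1.0. Simulated r was 0.96, 0.94 and 0.89.

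- b = 1: (1 − b)² = 0, so there is no loss at any skew.
- s = 0.7, b = 0.4, σ = 0.7: 0.36 × 0.307 × (1 − 0.938²)/0.49 = 0.027, SE ratio 1.013 (simulated 1.015).
- s = 1.0, b = 0.4, σ = 0.7: 0.36 × 0.540 × (1 − 0.893²)/0.49 = 0.080, SE ratio 1.039 (simulated 1.044).
- s = 1.0, b = 0.4, σ = 0.5: 0.36 × 0.540 × (1 − 0.893²)/0.25 = 0.158 (simulated variance +17%).

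**Step 3: simulation.** Increase in the variance of the treatment effect, raw versus log baseline:

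| Log-log slope | Site omitted, σ 0.6-0.8 | Site in model, 0.4 rule applied | Combined |
|---|---|---|---|
| 1 | 0% | about 0% | about 0% |
| 0.7 | 0-3% | 0-5% | 0-5% |
| 0.5 | 1-8% | 1-7% | 1-8% |
| 0.3 | 3-15% | 2-11% | 2-15% |

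In SE terms the upper ends are √1.05 = 1.025, √1.08 = 1.039 and √1.15 = 1.072. The +17% case in Step 2 lies outside these ranges because it combines the widest baseline with a smaller residual SD. A lower slope there would push it further.

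**Step 4: weight of extreme subjects.** Under the Step 2 distributions, the three most extreme of 60 subjects carry 43%, 51% and 61% of the covariate's sum of squares on the raw scale, against 25%, 26% and 28% on the log scale (s = 0.5, 0.7, 1.0).

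**Step 5: validity and power.** Bias was at most about 0.01 on the log scale and type I error about 5% with either covariate. At an assumed ratio of 0.65, power was typically 0 to 2.5 points lower with raw baseline, and at most about 6 points lower (79% against 85%).

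**The case against.** **A reader might infer that the adjustment is wrong and the result unreliable.** The documents do not support that. Randomisation protects the comparison, and bias and type I error were unaffected. Raw adjustment also matched or beat no adjustment to within 0.01 in relative SE.

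**A reader might infer that precision is lost and that a few subjects drive the answer.** Both statements need a baseline distribution and a slope that the documents do not give. At slope 1 nothing is lost. Leverage figures need particular care. A single count of 120 per week among 60 subjects has a raw leverage near 0.46-0.48 only when baseline is narrow, and then the chance that any of the 60 exceeds 120 is about 6%. With a wide baseline its leverage falls to about 0.22-0.28. Leverage on the baseline slope is also not leverage on the randomised contrast.

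**A simulation built on a log-linear relation favours log baseline.** This is a fair criticism of the first simulation column. However, log baseline was never materially worse even when the Week 8 mean was made linear in the raw count, with site in the model and the 0.4 rule applied. The predictive mean matching used for the ITT analysis was not modelled, so the sizes remain approximate.

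**The SAP does not say that the covariate is raw.** That stands: it is the natural reading, not a statement. The SAP 6.2 rule also covers the absolute-change models (6.9 points 2 and 4), where a raw baseline suits the response, so that sentence is not itself an error.

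**Efficacy is secondary and exploratory.** This also stands, and it limits the severity.

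**Conclusion.** The point holds as a conditional matter of efficiency and coherence. On its natural reading, SAP 6.9 point 1 pairs a log-ratio response with an untransformed count. The likely cost is an SE larger by about 0 to 4%. It reaches roughly 7 to 8% only with a wide baseline combined with a weak baseline-to-endpoint relation or a small residual SD. These sizes rest on assumed log-normal baselines truncated at 7, assumed slopes and assumed residual SDs.

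The equivalence in Step 1 rests on no such assumption: only log baseline makes the treatment estimate independent of whether the response is written as a log ratio or as log Week 8. The choice is also not neutral in a given dataset. At slopes below 1 the raw-adjusted and log-adjusted estimates differed with an SD of 0.015 to 0.07 against an SE of about 0.19, which is 8 to 37% of an SE. That is reason to state the scale before unblinding. Severity is low: no conclusion on the primary safety objective depends on it.

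**What to change.** In SAP 6.9 point 1, state that the covariate is the natural log of the total number of incontinence episodes in the 7 days before Visit 2. Apply the existing 0-to-0.4 rule to any zero baseline. Eligible subjects have at least 7 episodes, but SAP 4.1 accepts 0 as a valid Visit 2 count, so an eligibility deviation could produce one.

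Carry the same wording to the log-ratio analyses that refer to point 1: 6.9.1 points 1, 3 and 5, and 6.9.2 point 1. For nocturia (6.9 point 5), use the log of the baseline nocturia count, with the 0.4 rule stated explicitly because no entry minimum applies to nocturia. Keep the untransformed baseline for the absolute-change analyses (6.9 points 2 and 4). In 6.2, add that the baseline covariate is on the same scale as the response.

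The cost is one phrase in each place and one line of code. No new data are needed. In the scenarios tried, log baseline lost essentially nothing when the slope is 1.

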6.3 General Methodology

Safety

Safety data will be presented and analysed using the Safety Population.

The primary safety analyses include all treatment emergent adverse events defined as any AE started after Visit 2. The analysis will be carried out with point estimates and Clopper Pearson 95% confidence intervals.

Descriptive statistics will be provided for all variables in the summary tables by treatment group according to the type of variable summarised.

Quantitative variables will be summarised by using n (number of subjects per group), arithmetic mean, standard deviation (SD), median and range (minimum and maximum).

Categorical variables will be summarised by using frequency distributions and percentages.

The number of Adverse Events and the number and the percentage of patients experiencing those events, will be summarised by treatment group. Differences between groups will be evaluated using Chi-square test or Fisher's exact test. Subgroup analysis of differences between groups of AEs will be performed separately for patients who had an adverse event while on the 10mg dose (AE started from Visit 2 and Visit 3), 20 mg dose (AE started from Visit 3 and Visit 4) and 30 mg dose (AE started from Visit 4 and Visit 6). Subjects with adverse events who deviated from the protocol dosage will be highlighted in the footnotes.

Shift tables will be used to describe the evaluation of clinical significance for laboratory values, 12-Lead ECG and physical examination.

For all analyses, hypothesis testing will be carried out at the alpha = 0.05 level (two-sided) when comparing treatments. P-values will be rounded to three decimal places. Statistical significance will be declared if the rounded p-value will be less than or equal to 0.05.

Efficacy

For the PP efficacy analysis of incontinence episodes, only valid efficacy endpoints at Visit 6 will be used. For the ITT efficacy analysis of incontinence episodes, valid and imputed endpoints at Visit 6 will be used. The imputation method is described in section 6.1. No LOCF from baseline will be used for any efficacy analysis.

Descriptive statistics will be provided for all variables in the summary tables by treatment group according to the type of variable summarised.

Quantitative variables will be summarised by using n (number of subjects per group), arithmetic mean, standard deviation (SD), median and range (minimum and maximum).

Categorical variables will be summarised by using frequency distributions and percentages.

For all analyses, hypothesis testing will be carried out at the alpha = 0.05 level (two-sided) when comparing treatments. P-values will be rounded to three decimal places. Statistical significance will be declared if the rounded p-value will be less than or equal to 0.05.

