2 STUDY OBJECTIVES

2.1 Primary Objective

The primary objective of this study is to evaluate the safety and tolerability of litoxetine (dose titration 10 mg, 20 mg, 30 mg) compared to placebo administered orally twice daily (BID) for 8 weeks in subjects with a diagnosis of UI.

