8.10 Determination of Sample Size

Approximately 95 subjects are expected to be enrolled into the 2-week, single-blind (subject blind) Screening Placebo Run-In Period. It is expected that 20% of subjects will not qualify for randomization after Screening Placebo Run-In.

The study is expected to randomize approximately 78 subjects into the double-blind treatment where subjects will be allocated to litoxetine (dose titration over 10 mg, 20 mg, 30mg) or matched placebo BID in a 2:1 ratio. A post randomisation dropout rate of 30% has been estimated, resulting in 60 evaluable subjects.

This sample size will provide confidence intervals for the rate of safety events that are +/- 14% for the widest observed intervals in the treatment arm.

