2.1 Primary Objective

The primary objective of this study is to evaluate the safety and tolerability of litoxetine (dose titration 10 mg for 1 week - 20 mg for 1 week - 30 mg for 6 weeks BID) compared to corresponding placebo in subjects with a diagnosis of UI.

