3.1 Sample Size

Approximately 95 subjects are expected to be enrolled into the 2-week, single-blind (subject blind) Screening Placebo Run-In Period. It is expected that 20% of subjects will not qualify for randomization after Screening Placebo Run-In.

The study is expected to randomize approximately 78 subjects into the double-blind treatment where subjects will be allocated to litoxetine (dose titration over 10 mg, 20 mg, 30mg) or matched placebo BID in a 2:1 ratio. A post randomisation dropout rate of 30% has been estimated, resulting in 60 evaluable subjects.

A sample size of 60 subjects is expected to provide a 95% confidence interval for a rate of safety events of 50% with a width +/- 14%. The sample size calculation is based on the precision of the estimate of the primary outcome, safety events, using a rate of 50% which would provide the most conservative sample size.

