6.8 Additional Safety Analyses

Adverse Events

The number of treatment-emergent AEs, non-TEAEs, AEs occurring during follow-up or following discontinuation, AEs leading to death, AEs leading to discontinuation and SAEs, and the number and the percentage of patients experiencing those events, will be summarised by treatment group. Differences between groups will be evaluated using Chi-square test or Fisher's exact test (if more than 20% of the cells in a contingency table have counts less than 5).

The following adverse events will be specifically summarized by treatment:

1. TEAEs of Special Interest include urinary retention, psychiatric adverse events (nervousness, anxiety, panic attacks, insomnia, aggression, mania, suicidal ideation, development/worsening of depression) and withdrawal symptoms
2. Treatment Emergent Suicidal Adverse Events and Adverse Events suggestive of abuse potential
3. SAEs
4. TEAEs
5. Non-TEAEs
6. AEs/SAEs which occurred during the 30-day Follow-up Period or following discontinuation

The SOCs and PTs will be used for tabulation. The number of AEs and the number and the percentage of patients with at least one AE will be presented by SOC and PT for each treatment group. Within each SOC and PT, the highest severity grade attained will be reported, for AEs with divergent severities.

A comparison of treatment-emergent AE rates between lítoxetine and placebo will be performed using an exact logistic regression model with the treatment-emergent AE ("1"=At least one treatment-emergent AE occurred for the patient; "0"=otherwise) as dependent variable and lítoxetine dose as fixed effects. The probability modelled will be treatment-emergent AE="1".

The number of patients and the number of patients considered in the model will be provided. The exact odds ratio of the fixed effects will be calculated as the number of patients with/without AEs in all arms. If the omnibus test is significant, comparisons between arms will be tested individually, with the relative 95% CI and p-value.

The same model will be repeated by considering SAE ("1"=At least one SAE occurred for the patient; "0"=otherwise) as dependent variable.

AEs leading to study drug discontinuation and AEs leading to death will be presented in the listings only.

SAEs will be listed and summarised in a table, including a description of each event, the time to onset, the severity, and the relationship to trial drug.

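### For adverse events, the SAP gives a between-arm confidence interval only after a significant test, although the primary objective compares litoxetine with placebo

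*SAP*

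**What the plan says.** Both documents make the primary objective comparative. Protocol 2.1 asks for safety and tolerability "compared to placebo administered orally twice daily (BID) for 8 weeks in subjects with a diagnosis of UI", and SAP 2.1 for the titration regimen "compared to corresponding placebo in subjects with a diagnosis of UI". Protocol 8.10 states: "The study is expected to randomize approximately 78 subjects into the double-blind treatment", allocated to litoxetine or "matched placebo BID in a 2:1 ratio".

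The primary analysis of adverse events is descriptive within each arm. SAP 6.3 says: "The analysis will be carried out with point estimates and Clopper Pearson 95% confidence intervals". SAP 6.7 item 1 repeats this for TEAEs by treatment group and calls them the primary safety endpoint.

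SAP 6.3 and 6.8 compare arms by a chi-square or Fisher test at two-sided 0.05. SAP 6.8 adds an exact logistic model for any TEAE, repeated for any SAE, from which an exact odds ratio is calculated. Its interval is conditional: "If the omnibus test is significant, comparisons between arms will be tested individually, with the relative 95% CI and p-value".

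Other primary safety endpoints carry no such condition. SAP 6.7 item 6 reports a p-value and 95% CI for the blood-pressure comparison, and SAP 6.8 reports the QT and QTc comparison with placebo by 95% CI.

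On size, SAP 3.1 says that 60 subjects "is expected to provide a 95% confidence interval for a rate of safety events of 50% with a width +/- 14"%. Protocol 8.10 and SAP 1.6 attach the same figure to the treatment arm.

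**The concern.** Two per-arm intervals do not form an interval for the difference, and a p-value does not show how large an excess the data still allow. The one between-arm interval planned for adverse events depends on a significant omnibus test. With two randomised arms, the omnibus test and the individual comparison are the same test. The interval is therefore printed when the excess has already been declared, and left out when the reader most needs to know what has not been excluded.

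At stake is how a non-significant result is read. In a trial of this size, an adverse-event comparison that misses 0.05 can be taken as evidence of similar safety while a large excess remains compatible with the data.

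**Working it through.** **Inputs.** 78 randomised 2:1 (Protocol 8.10): 78 × 2/3 = 52 litoxetine and 26 placebo. The Safety Population is all randomised subjects who receive study drug and have at least one visit (Protocol 8.2), so up to 52:26. The stated 60 evaluable subjects split 40:20. Two-sided alpha is 0.05, with p-values rounded to three decimals before comparison (SAP 6.3). The only event rate in the documents is the 50% worst case; every other rate below is an assumption.

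**Step 1: the plan's own figure.** Half-width for one rate at 50%:
- n = 52: 1.96 × √(0.25/52) = 13.6 points (Wald); Clopper-Pearson 14.2. This reproduces ±14 for the litoxetine arm.
- n = 60, as SAP 3.1 has it: 12.7 (Wald), 13.2 (Clopper-Pearson), so about ±13.
- n = 26, the placebo arm: Clopper-Pearson 20.1.

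**Step 2: precision of the difference.** Wald half-width 1.96 × √[p(1−p)(1/n₁ + 1/n₂)]:

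| Rate in both arms | 52:26 | 40:20 |
|---|---|---|
| 50% | 23.5 | 26.8 |
| 30% | 21.6 | 24.6 |
| 20% | 18.8 | 21.5 |

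The Newcombe half-width at 50% is 22.2 for 52:26 and 24.9 for 40:20. The difference is thus estimated to roughly ±19 to ±27 points, and to ±22 to ±24 at 50% with 52:26.

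**Step 3: how often the test is significant.** Exact enumeration of both binomials at 52:26, rejecting when the rounded p-value is 0.050 or less:

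| Litoxetine vs placebo | Fisher | Chi-square |
|---|---|---|
| 50% vs 30% | 33% | 39% |
| 70% vs 50% | 36% | 42% |
| 60% vs 30% | 65% | 71% |
| 50% vs 20% | 72% | 75% |
| 80% vs 50% | 72% | 79% |

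The condition in SAP 6.8 refers to an exact logistic model, and Fisher's test is the nearer stand-in for it. On that basis, at 50% vs 30%, about 100 − 33 = 67% of trials would show no between-arm interval.

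**Step 4: an example.** Take 26/52 (50.0%) vs 8/26 (30.8%), an excess of 19.2 points. Fisher p = 0.147 and chi-square p = 0.106. The Wilson limits are 36.9–63.1% and 16.5–50.0%. The Newcombe interval follows:
- lower: 19.2 − √[(50.0 − 36.9)² + (50.0 − 30.8)²] = 19.2 − 23.2 = −4.0
- upper: 19.2 + √[(63.1 − 50.0)² + (30.8 − 16.5)²] = 19.2 + 19.4 = 38.6

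The plan would print both percentages, their Clopper-Pearson intervals (35.8–64.2% and 14.3–51.8%), an odds ratio (the simple estimate is 26 × 18 / (26 × 8) = 2.25) and a non-significant p-value. It would not print any interval for the odds ratio or the difference.

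**The case against.** The strongest reply is that this is a small Phase I/IIa trial whose primary analysis is openly descriptive. Protocol 8.1 says that the primary analyses describe adverse events, and SAP 3.1 says that the size rests on the precision of a rate. No power is claimed. That stands: precision-based sizing is a declared choice, and nothing here makes it an error.

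Several stronger readings are tempting, and the documents do not support them.
- *The p-value would stand alone.* It would not. Counts, percentages and Clopper-Pearson intervals are tabulated by arm, and the calculation of the odds ratio has no stated condition. A reader could derive a risk-difference interval from the counts. What is missing is the displayed between-arm interval.
- *The ±14% is offered as comparative precision.* Protocol 8.10 and SAP 1.6 label it as treatment-arm precision, and SAP 3.1 speaks of a single rate.
- *The conditional interval is the one of about ±24 points.* The conditional interval belongs to an odds ratio. A risk-difference interval is not planned under any outcome.
- *A real excess would usually be missed.* That holds for excesses of about 20 points, but a 30-point excess would usually be detected.
- *The comparative objective has no interval estimate at all.* Blood pressure and QT/QTc have unconditional intervals; the gap concerns adverse events.

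The descriptive character of the trial is, if anything, a reason to show the interval always. It does not explain why the SAP tests at 0.05 and makes the interval depend on that test.

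**Conclusion.** The point holds for adverse-event rates. The primary objective is comparative, and SAP 6.7 names TEAEs as the primary safety endpoint. Yet the plan has no risk-difference interval for them, and its one between-arm interval is suppressed by rule when the comparison is not significant. For a moderate true excess (50% vs 30%) suppression is the likely outcome, in about two-thirds of trials by the Fisher figure; for a 30-point excess it is the less likely one.

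This rests on assumed event rates, on a Safety Population close to 52:26, and on reading dose in the SAP 6.8 model as randomised arm, which fits the two-arm design. The per-arm results remain valid. The defect is in reporting and should be corrected; it does not invalidate the design or its size.

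**What to change.** 1. In SAP 6.8, delete the condition on the omnibus test, so that the exact odds ratio for any TEAE and any SAE always carries its 95% CI.
2. In SAP 6.3, 6.7 and 6.8, report the litoxetine minus placebo risk difference with a two-sided 95% score-type interval (Newcombe or Miettinen-Nurminen), whatever the test result. Do so for any TEAE, SAEs, AEs of interest, AEs of psychiatric interest, and AEs leading to discontinuation. Keep the per-arm Clopper-Pearson intervals. For discontinuations, SAP 6.8 both summarises the events by arm and says that they are listed only; the new column needs the by-arm summary.
3. Optionally, in SAP 3.1, restate that ±14% applies to the litoxetine arm of about 52, as Protocol 8.10 has it, and not to 60 subjects (about ±13). Add that the between-arm difference is estimated to roughly ±19 to ±27 points, depending on the event rate and the number analysed (about ±22 to ±24 at 50% with 52:26).

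The cost is SAP wording and one extra column in the adverse-event tables. No new data or subjects are needed. The downside is that the stated comparative precision looks less favourable than ±14%.
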